**Measure Analysis Population Description**

The sample size was calculated with the population size is 280 patients who attend to Renal Health Clinic, considering that the incidence of subclinical hypothyroidism in grade 3-4 CKD is between 8 to 17,9% a confidence (1-alpha) of 95% = 1.96 and an error rate of 1, the desired population is 50 patients, with 50% distribution, the recommended sample is 13 to 25 patients in each intervention group.

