**Number of Baseline Participants**

38 patients ( 19 arm Levothyroxine and 19 arm placebo)

**Number of Units Analyzed** 32 patients ( 18 arm Levothyroxine and 14 arm placebo)

**Analysis Population Type** Participants

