### Primary Outcome Measure:

1. 24 hours urine Proteinuria in patients with subclinical hypothyroidism and CKD G2-G5 without renal support therapy Randomized clinical trial of levothyroxine group versus placebo [Time Frame: three months]

Outcome Measure Description. Definition: Proteinuria was defined as the presence of proteins in the urine for 24 hours with a range greater than or equal to 0.150 grams / 24 hours. A measurement was made at the beginning and at 3 months of the study to all patients

Measure Type: mean

Measure of Dispersion/Precision: Standard Deviation

Number of Participants Analyzed: 32patients

Number of Units Analyzed: (18 arm Levothyroxine and 14 arm placebo)

Unit of Measure: grams/ 24 hours

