### **Statistical Test of Hypothesis and Method**

In the case of quantitative variables, the data are shown as average or median with standard deviation, according to the distribution, be it parametric or non-parametric, respectively.

The nominal variables are shown with frequencies or percentages.

For intergroup and continuous variable comparisons, in the case of qualitative variables, chi2 and, in the case of quantitative variables, the Student's T test or Mann-Whitney U test depending on the distribution of the sample.

The statistical analysis will be carried out with the statistical program SPSS, version 20.

In all cases a value of  $p < 0.05$  will be accepted as significant.

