### **Method of Estimation (or Statistical Test of Hypothesis or Other Statistical Analysis required)**

- Mean Difference (Final Values)
  - Risk Ratio (RR) (Adverse effects)

**Parameter Dispersion Type :** Standard Deviation

Adverse Event Information

All-Cause Mortality: no death

Eventos adversos graves: no serious adverse event

Other (Not Including Serious) Adverse Events:

During the study the following adverse effects were presented: Urinary tract infection in a single patient of the placebo group (7.14%) and nervousness in two patients of the levothyroxine group (11.11%) (RR 1.55 95% CI (0.15-15.47), value p = 1.0).

None left the study because of the adverse effect. Adverse events were not severe according to the severity scale

Table of non-serious adverse events		
arm Levothyroxine	(N=1) 7.14%	Infections and Infestations (Urinary tract infection)
Arm placebo	(N=2) 11.11%	Psychiatric Disorder (Anxiety)

Duration of urinary tract infection: five days, without complications.

Anxiety duration time: three days, without complications.

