### **Overall Limitations and Caveats**

Overall Limitations and Caveats At least 12 to 25 patients are needed in each arm.

There were missed follow-ups in both arms but more in the placebo arm.

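### The only stated sample size comes from the frequency of subclinical hypothyroidism, so it does not size the primary comparison of 24-hour proteinuria

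*Combined protocol and SAP*

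**What the plan says.** All places are in the combined protocol and SAP.

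- **Measure Analysis Population Description** gives the sizing. Its inputs are a clinic population of 280, a frequency and confidence level ("considering that the incidence of subclinical hypothyroidism in grade 3-4 CKD is between 8 to 17,9% a confidence (1-alpha) of 95% = 1.96"), plus a precision term given as "an error rate of 1", with no unit. Its result: "the desired population is 50 patients, with 50% distribution, the recommended sample is 13 to 25 patients in each intervention group".
- **Overall Limitations and Caveats** restates the result as a requirement: "At least 12 to 25 patients are needed in each arm".
- **Primary Outcome Measure** is "24 hours urine Proteinuria in patients with subclinical hypothyroidism and CKD G2-G5 without renal support therapy", levothyroxine against placebo at three months, in grams per 24 hours.
- **Statistical Analyses** gives the type of test as superiority. **Statistical Test of Hypothesis and Method** specifies Student's t or Mann-Whitney U according to distribution, at p < 0.05.
- **Method of Estimation** lists a mean difference in final values, with standard deviation as the dispersion type. It plans no confidence interval for that difference.
- **Number of Baseline Participants** gives 38 patients (19 per arm) at baseline and 32 analysed: "18 arm Levothyroxine and 14 arm placebo".

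**The concern.** Subclinical hypothyroidism is what brings a patient into this trial; it is not the outcome. Its frequency helps to say how many eligible patients the clinic might yield, or how precisely that frequency could be estimated. It carries no information on how many patients are needed to tell two arms apart on proteinuria. For that, a calculation needs a target difference, an SD and a power, and the documents state none of these as planning inputs.

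The figure is nevertheless the only sample-size yardstick in the documents, and it is described first as recommended and then as needed. Both analysed arms lie above its lower end, whether that is 12 or 13, and below its upper end of 25. A reader could infer adequacy from the first fact or inadequacy from the second, and neither inference is sound. The practical risk is in interpretation: with significance judged at p < 0.05 and no interval planned, a non-significant proteinuria result could be read as no effect.

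**Working it through.** **1. Can the stated figure be reproduced?**

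The formula is not given, so three routes were tried. Two use the usual finite-population formula for one proportion: n = N·x / ((N − 1)·E² + x), with x = 1.96²·p(1 − p).

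| Route | Lower end | Upper end |
|---|---|---|
| Plain count, 280 × frequency | 280 × 0.08 = 22.4 in total, 11.2 per arm (12 rounded up) | 280 × 0.179 = 50.1 in total, 25.1 per arm |
| Formula, N = 280, E = 0.10 (assumed) | 280 × 0.2827 / (279 × 0.01 + 0.2827) = 25.8, so 26 in total, 13 per arm | 280 × 0.5646 / (279 × 0.01 + 0.5646) = 47.1, so 48 in total, 24 per arm |
| Formula, N = 50, p = 0.50, E = 0.01 | not applicable | 50 × 0.9604 / (49 × 0.0001 + 0.9604) = 49.7, so 50 in total, 25 per arm |

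The first or third route explains 50 in total and 25 per arm. An assumed 10-point error gives 13 at the lower end, and the plain count gives 12. An error of 1% with N = 280 gives 255 to 267 in total, far from the stated figure. The derivation is therefore under-specified, but every route that comes close uses only frequency and precision inputs.

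**2. What the primary comparison would need**

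| Input | In the sizing statement | Elsewhere in the documents |
|---|---|---|
| Target difference in proteinuria | no | no |
| Planning SD of proteinuria | no | no; only observed baseline SDs in Table 1 |
| Power | no | no |
| Significance level | 95% confidence, z = 1.96 | p < 0.05 |

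No correct sample size can be calculated from the documents, because the target difference and the power are missing.

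**3. Illustration, calculated afterwards**

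Assumptions: t test, two-sided 5%, 80% power, and Table 1 proteinuria SDs as printed (1.28 placebo, n = 14; 1.20 levothyroxine, n = 18), standing in for the SDs at three months.

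- Pooled SD = √((13 × 1.28² + 17 × 1.20²)/30) = 1.235 g/24h.
- Pooled baseline mean = (14 × 1.28 + 18 × 1.71)/32 = 1.52 g/24h.
- Detectable difference from the noncentral t distribution: 1.48 g/24h at 12 per arm, 1.41 at 13 per arm, 1.27 at 14 v 18, and 1.00 at 25 per arm.
- 95% CI half-width at 14 v 18 = 2.042 × 1.235 × √(1/14 + 1/18) = 0.90 g/24h.

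Relative to the pooled baseline mean, 1.27 is 84% (1.27/1.52). The plan's own range of 12 to 25 per arm runs from 97% (1.48/1.52) to 66% (1.00/1.52).

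The result depends on the model. With lognormal data (mean 1.52, SD 1.235), a proportional reduction and the Mann-Whitney test at 14 v 18, simulated power is about 72% for a reduction of 0.76 g/24h and 91% for 0.91 g/24h. The 80% point is therefore about 0.8 g/24h.

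**The case against.** The case against making much of this has several parts.

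- **No calculation error is shown.** This stands. The upper end follows from the document's own numbers. The fault is in the basis, not the arithmetic, and the difference between 12 and 13 is minor.
- **A reader might infer that the trial is underpowered.** The documents do not support that. They name no target difference, and under the t-test assumptions above 25 per arm gives about 80% power for 1.00 g/24h. Missing the upper end of 25 proves nothing either, because that number was not derived from proteinuria.
- **The 1.27 g/24h figure is fragile.** This stands. The SDs are nearly as large as the means of a positive variable, so skew is likely and the plan's own rule may select Mann-Whitney. Table 1 entries may also be medians, since "the data are shown as average or median with standard deviation". The figure is an illustration only.
- **The harm is hypothetical.** This stands in part. No section calls 18 and 14 adequate, the restated figure sits under limitations, and the documents report no three-month proteinuria result, so nothing has yet been misread. The trial is also completed, so the number cannot change. What remains is a requirement worded as needed that has no connection to the primary endpoint.

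Nor does this point settle whether the comparison is otherwise sound. Losses were 5 of 19 on placebo and 1 of 19 on levothyroxine, which is a separate question.

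**Conclusion.** The concern holds as a statement about the basis of the sample size. The only figure in the documents, 50 in total and 13 (or 12) to 25 per arm, comes from the clinic population, the frequency of an eligibility condition and a precision term. It does not size the superiority comparison of 24-hour proteinuria and cannot show whether 18 and 14 are enough. That conclusion can be read directly from the text and rests on no assumption.

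The size of the consequence does rest on assumptions. At 14 v 18 the detectable difference is about 1.27 g/24h under the t-test model and about 0.8 g/24h under the lognormal Mann-Whitney model. Because the trial is finished and the correction is cheap, the documents should be corrected, but the point is no ground for saying that the trial failed or was too small.

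**What to change.** Leave enrolment as it is and change three sections.

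1. **Measure Analysis Population Description:** state that the calculation is based on frequency, that it does not size the proteinuria comparison, and that no endpoint-based calculation is documented. Give the formula and the unit of the error rate if they are on record.
2. **Overall Limitations and Caveats:** keep the figure on record, but annotate it as not being a requirement for the primary endpoint. Reconcile 12 with 13, and state that the trial was not sized for 24-hour proteinuria.
3. **Method of Estimation:** add a 95% CI for the between-group difference in three-month proteinuria. State that a non-significant result is not evidence of no effect unless that CI excludes relevant differences.

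Optionally, report the detectable difference and half-width at 14 v 18 (about 1.27 and 0.90 g/24h). Mark them as calculated afterwards and dependent on the model, with the 0.8 g/24h alternative beside them.

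The cost is rewording three sections, one extra interval and a less favourable statement about sample size. No patients are added.

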## Outcome Measures

---

### Primary Outcome Measure:

1. 24 hours urine Proteinuria in patients with subclinical hypothyroidism and CKD G2-G5 without renal support therapy Randomized clinical trial of levothyroxine group versus placebo [Time Frame: three months]

Outcome Measure Description. Definition: Proteinuria was defined as the presence of proteins in the urine for 24 hours with a range greater than or equal to 0.150 grams / 24 hours. A measurement was made at the beginning and at 3 months of the study to all patients

Measure Type: mean

Measure of Dispersion/Precision: Standard Deviation

Number of Participants Analyzed: 32patients

Number of Units Analyzed: (18 arm Levothyroxine and 14 arm placebo)

Unit of Measure: grams/ 24 hours

### Secondary Outcome Measures:

1. Estimated glomerular filtration rate (eGFR) in patients with subclinical hypothyroidism and CKD G2-G5 without renal support therapy Randomized clinical trial of levothyroxine group versus placebo [Time Frame: three months]

Outcome Measure Description [\*] Definition: Outcome Measure Description [\*]

Definition: the glomerular filtration rate was calculated based on the seric creatinine expressed in mg / dl, the formula of CKD-EPI was use.

Measure of Dispersion/Precision: Standard Deviation

Number of Participants Analyzed: 32patients

Number of Units Analyzed: (18 arm Levothyroxine and 14 arm placebo)

Unit of Measure eGFR ml/min/1.73m^2

2. Measurement of lipid profile (cholesterol, LDL and triglycerides) in patients with subclinical hypothyroidism and CKD G2-G5 without renal support therapy Randomized clinical trial of levothyroxine group versus placebo. [Time Frame: three months]

Outcome Measure Description.

Definition: serum cholesterol, triglycerides and LDL cholesterol levels were measured in mg / dl at the beginning and at the end of three months for all patients

Measure of Dispersion/Precision: Standard Deviation

Number of Participants Analyzed: 32patients

Number of Units Analyzed: (18 arm Levothyroxine and 14 arm placebo)

Unit of Measure mg/dl

## **Statistical Analyses**

- **Type of Statistical Test:** Superiority

### **Statistical Test of Hypothesis and Method**

In the case of quantitative variables, the data are shown as average or median with standard deviation, according to the distribution, be it parametric or non-parametric, respectively.

The nominal variables are shown with frequencies or percentages.

For intergroup and continuous variable comparisons, in the case of qualitative variables, chi2 and, in the case of quantitative variables, the Student's T test or Mann-Whitney U test depending on the distribution of the sample.

The statistical analysis will be carried out with the statistical program SPSS, version 20.

In all cases a value of  $p < 0.05$  will be accepted as significant.

### **Method of Estimation (or Statistical Test of Hypothesis or Other Statistical Analysis required)**

- Mean Difference (Final Values)
  - Risk Ratio (RR) (Adverse effects)

**Parameter Dispersion Type :** Standard Deviation

Adverse Event Information

All-Cause Mortality: no death

Eventos adversos graves: no serious adverse event

Other (Not Including Serious) Adverse Events:

During the study the following adverse effects were presented: Urinary tract infection in a single patient of the placebo group (7.14%) and nervousness in two patients of the levothyroxine group (11.11%) (RR 1.55 95% CI (0.15-15.47), value p = 1.0).

None left the study because of the adverse effect. Adverse events were not severe according to the severity scale

Table of non-serious adverse events		
arm Levothyroxine	(N=1) 7.14%	Infections and Infestations (Urinary tract infection)
Arm placebo	(N=2) 11.11%	Psychiatric Disorder (Anxiety)

Duration of urinary tract infection: five days, without complications.

Anxiety duration time: three days, without complications.

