## **6. Detailed Description:**

Thyroid disorders, especially elevated TSH levels in patients with CKD, are frequent. As it is an easy medication to acquire and of little cost compared to the other options, levothyroxine would provide benefits already known in patients with CKD and also a proteinuria effect (knowing each other). as a factor of progression of the CKD a health problem worldwide) being a potentially useful treatment and a dose that the risk is minimal. The study consists of 3 phases, the first phase consists of capturing patients from the renal health clinic, having baseline measurement of the variables. Then, the second phase consists of both groups treating them with medication (levothyroxine with a safe dose for the investigator's population with high cardiovascular risk of 0.25mcg so that the patient's weight range between 50-80kg maintains a dosage of 0.3-0.5mcg / kg / day that the thyroid axis is not affected) of fasting levothyroxine (in the case of taking a drug that interacts with absorption changes its use according to the specified hours, see Table 2) or placebo according to the randomization 1: 1 for three months and that have treatment with ACEI or ARA-2 (specifying which and the dose thereof), with follow-up every 4 weeks (Monitoring thyroid function). The third phase consists of a comparison of the variables studied.

The primary objective is to evaluate the effect of the use of levothyroxine on the levels of proteinuria measured on the test strip of the general urine and protein examination in 24-hour urine patients with chronic kidney disease without renal support therapy with proteinuria, who already receive the standard antiproteinuric treatment with an ACE inhibitor or ARA-2 against placebo and the secondary objectives are to evaluate the changes in proteinuria, according to TSH levels in 2.5-9.9  $\mu\text{iml / L}$ , with the levels of T4L in levels 0.8-1.8mcg / ml), analyze improvement in glomerular filtration rate in patients receiving levothyroxine and at the end of the study and evaluate Tolerability and safety of levothyroxine as antiproteinuric treatment in chronic kidney disease without renal support therapy, and as secondary objectives improvement in cholesterol, triglycerides blood pressure. Any adverse event will be recorded in the adverse event reporting forms. (definition of the International Conference on Harmonization [ICH])

- Study Type: Interventional

Actual Enrollment: 32 participants

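### Three-month final values are compared without baseline adjustment, although the 32 analysed patients differ at baseline, most of all on LDL

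*Combined protocol and SAP*

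**What the plan says.** Under Method of Estimation, the only estimate named for the continuous outcomes is "Mean Difference (Final Values". Statistical Test of Hypothesis and Method gives the matching test as a Student's "T test or Mann-Whitney U test depending on the distribution of the sample". No section names a change score, a baseline covariate or ANCOVA.

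The baseline data exist. Section 6 (Detailed Description) says the first phase consists of enrolling patients and "having baseline measurement of the variables". For 24-hour protein, "A measurement was made at the beginning and at 3 months of the study to all patients". For lipids, "levels were measured in mg / dl at the beginning and at the end of three months for all patients".

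The primary objective concerns the "effect of the use of levothyroxine on the levels of proteinuria", which fits a final-value comparison. The secondary objectives in the same section speak of changes in proteinuria by TSH level, and of improvement in filtration rate, cholesterol and triglycerides. No method is attached to them.

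The baseline count is "38 patients ( 19 arm Levothyroxine and 19 arm placebo", but Table 1 describes only the 14 placebo and 18 levothyroxine patients analysed. Overall Limitations and Caveats adds: "There were missed follow-ups in both arms but more in the placebo arm".

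**The concern.** A comparison of final values ignores where each arm started. Randomisation makes that harmless on average, but this analysis set lost 5 of 19 placebo and 1 of 19 levothyroxine patients, and its arms differ at baseline on several measured outcomes. Whatever part of a baseline gap persists to 3 months is then read as a drug effect.

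Two things are at stake. For LDL, an inert drug could appear harmful. For proteinuria, the primary outcome, the estimate is pulled against levothyroxine and the chance of detecting a real fall drops, in a trial whose sample-size statement gives no effect size, SD or power.

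**Working it through.** **Inputs.** Means and SDs from Table 1 (14 placebo, 18 levothyroxine). The correlation r between baseline and 3 months is not in the documents; I assume 0.3, 0.5, 0.7 and 0.9. The 3-month SD is assumed equal to the pooled baseline SD, and tests are taken as two-sided.

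**1. Baseline gaps (levothyroxine minus placebo).** Pooled SD = √[(13·SD₀² + 17·SD₁²)/30]; SE = SD·√(1/14 + 1/18) = 0.356·SD. For LDL: gap 102.38 − 75.5 = 26.88, SD 26.76, SE 9.53, t = 2.82, p = 0.008. The printed p of 0.01 is reproduced.

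| Variable | Gap | SD | Gap/SD | t-test p | Printed p |
|---|---|---|---|---|---|
| LDL (mg/dl) | +26.88 | 26.76 | 1.00 | 0.008 | 0.01 |
| TSH | +1.47 | 1.99 | 0.74 | 0.047 | 0.02 |
| Creatinine (mg/dl) | −1.19 | 1.38 | −0.86 | 0.022 | 0.05 |
| Triglycerides (mg/dl) | −49.3 | 85.0 | −0.58 | 0.11 | 0.09 |
| 24-h protein (g) | +0.43 | 1.24 | 0.35 | 0.34 | 0.14 |
| Cholesterol (mg/dl) | −5.07 | 54.2 | −0.09 | 0.79 | 0.67 |

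Some printed p-values may come from rank tests, which summary data cannot confirm. CKD G5 is 4/18 against 7/14 (Fisher p = 0.14). Losses are 1/19 against 5/19 (Fisher p = 0.18).

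**2. Expected shift with no drug effect** = r × gap, at r = 0.3/0.5/0.7/0.9:
- LDL: +8/+13/+19/+24 mg/dl (against levothyroxine).
- Protein: +0.13/+0.22/+0.30/+0.39 g (against levothyroxine).
- Triglycerides: −15/−25/−35/−44 mg/dl (in favour of levothyroxine).

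**3. False significance with no drug effect.** Normal simulation with baseline means and SDs fixed at Table 1; 20,000 runs (10,000 for triglycerides).
- LDL t-test: p < 0.05 in 12/24/47/86% of trials, nearly all with levothyroxine looking worse.
- Triglycerides t-test: 7/9/12/11%.
- Protein t-test: no inflation. A false benefit occurs in about 1% at r = 0.3 and in 0.3% or less from r = 0.5, against a nominal 2.5%.
- ANCOVA: 5% for every outcome.

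**4. Precision.** SE(ANCOVA) = SE·√[(1 − r²)·(1 + d²/3.81)], where d is gap/SD and 3.81 = 30·(1/14 + 1/18). The imbalance factor 1 + d²/3.81 is 1.265 for LDL and 1.032 for protein. The 95% half-widths are:
- LDL: 2.042 × 9.53 = 19.5 mg/dl for final values; 20.9/19.0/15.7/9.6 with ANCOVA.
- Protein: 2.042 × 0.440 = 0.90 g for final values; 0.87/0.79/0.65/0.40 with ANCOVA.

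Average half-widths in the simulation were about 1% smaller. With a 30/29 degrees-of-freedom factor, ANCOVA becomes more precise at r² > 1 − 1/(1.265 × 1.034), so r above about 0.49, for LDL. For protein the break-even is about 0.25.

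**5. Power for protein.** For an assumed fall of 0.85 g: t-test 35/26/14/2%, ANCOVA 49/56/73/99%. At r = 0.2 the figures are 40% and 48%. A levothyroxine mean of 1.71 − 0.85 = 0.86 g with SD 1.24 would imply 24% negative values, so the normal model is rough.

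**6. Skewed version (illustrative).** Log-normal simulation, 6,000 runs, arms matched to Table 1: log means −0.10 and 0.34, pooled log SD 0.73, so the gap of 0.44 is a ratio of 1.55. Power for an assumed halving: Mann-Whitney 52/37/21/3%, log-scale ANCOVA 73/81/93/100%; at r = 0.2, 59% and 72%. With no effect, Mann-Whitney rejects in 6/8/11/11%.

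**7. eGFR cannot be quantified.** The stage counts in Table 1 bound the means.
- Levothyroxine: (3·45 + 4·30 + 7·15 + 4·0)/18 = 20.0 to (3·60 + 4·45 + 7·30 + 4·15)/18 = 35.0, but 13.35 is printed.
- Placebo: (2·30 + 5·15 + 7·0)/14 = 9.64 to (2·45 + 5·30 + 7·15)/14 = 24.64. The printed 9.96 leaves 14 × 9.96 − 135 = 4.4 above the floor, so the seven G5 patients would average at most 4.4/7 = 0.6 ml/min.

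The row as printed gives t-test p = 0.70, against a printed 0.16. If means and SDs were interchanged, the means would be 18.3 and 28, which do fit the bounds, but p would be 0.03. Because other rows also fail to match a t-test, that mismatch does not rule the interchange out. Only source data can settle it.

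**The case against.** **The objectives imply change from baseline, and the t or Mann-Whitney rule could be applied to changes.** The wording is there, but no method is attached to it and the only named estimate is final values. The point stands as an inconsistency to resolve; it does not supply the adjustment. A plain change score would also over-correct, by (1 − r) × gap: for LDL at r = 0.5, 13.4 mg/dl in the other direction.

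**LDL is one part of a secondary outcome and has the largest gap; cholesterol is nearly balanced.** True. On the primary outcome the gap is modest and works against levothyroxine, so the risk there is a missed effect.

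**The protein power figures depend on assumptions.** Also true: the 0.85 g fall, the halving, r and the 3-month SD are not in the documents, and 2% against 99% needs r = 0.9 and the observed gap. Averaged over randomisations, the t-test has about 46% power for 0.85 g. With no gap and r = 0.5 the comparison is 46% against 58%. These figures deserve only moderate confidence.

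**The trial is complete, the unequal losses are disclosed and the LDL and TSH gaps are flagged.** This limits the remedy to a supporting analysis. Disclosure does not tell a reader how much of a 3-month difference is carry-over.

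**Conclusion.** The concern holds. The plan does not use baseline values that it collected, and the analysed arms differ at baseline. This is a problem of conditional accuracy and precision; it does not invalidate the primary test.

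Confidence is high that baseline is unused and that the LDL contrast is shifted against levothyroxine. The direction holds for any positive r, and the size is 8 to 24 mg/dl for r from 0.3 to 0.9. For protein, the shift is 0.13 to 0.39 g against levothyroxine. The power loss is small if r is low and large if r is high.

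The eGFR contrast probably leans towards levothyroxine, which has lower baseline creatinine and fewer G5 patients, but no figure is claimed. The documents cannot show whether chance or selective loss produced the gaps.

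**What to change.** - Analyse 3-month 24-hour protein, eGFR, LDL, cholesterol and triglycerides by ANCOVA on arm and the outcome's own baseline, with the adjusted difference and 95% CI. For protein, use the log scale and an adjusted ratio if residuals are skewed.
- Label this post hoc and show it beside the planned t or Mann-Whitney results, without replacing them.
- Correct the eGFR row of Table 1 and its p-value from source data before fitting the eGFR model.
- Give Table 1 for all 38 randomised patients.
- State that ANCOVA does not fully repair the unequal losses or the remaining imbalance in TSH and CKD stage.

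The cost is a re-run in SPSS on existing data, a corrected table and one degree of freedom per model. If r is low the gain is small, and the LDL interval could be slightly wider (20.9 against 19.5 mg/dl at r = 0.3).

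### The plan labels the dispersion of the between-arm mean difference as a standard deviation and plans no standard error or confidence interval for it; medians are also paired with an SD

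*Combined protocol and SAP*

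**What the plan says.** All places are in the combined protocol and SAP.

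- **Method of Estimation.** Two effect measures are listed: "Mean Difference (Final Values)" and "Risk Ratio (RR) (Adverse effects)". One dispersion line follows for the whole entry: "Parameter Dispersion Type : Standard Deviation". Under the same heading, the adverse-event comparison is given as "RR 1.55 95% CI (0.15-15.47)".
- **Statistical Test of Hypothesis and Method.** For quantitative variables, "the data are shown as average or median with standard deviation, according to the distribution, be it parametric or non-parametric, respectively". The between-arm comparison is by "the Student's T test or Mann-Whitney U test depending on the distribution of the sample", with significance at p < 0.05. No interval is attached to either test.
- **Primary Outcome Measure.** The measure type for 24-hour proteinuria is the mean, with "Measure of Dispersion/Precision: Standard Deviation", for 18 levothyroxine and 14 placebo patients. The Secondary Outcome Measures give SD in the same way.
- **Measure Analysis Population Description.** The only other mention of 95% confidence is here, as an input to the sample size and not as an interval for an effect.

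**The concern.** A mean difference between arms is an estimated parameter. Its uncertainty depends on the spread of the patients and on the arm sizes, and is expressed by a standard error or a confidence interval. The SD leaves out the arm sizes. Followed literally, the plan would put the wrong error bar on its primary effect estimate.

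In a trial that analysed 32 patients, the interval tells the reader which effects on proteinuria remain plausible, and a p-value alone does not. The document gives an interval for a safety comparison based on three events but plans none for the primary efficacy outcome.

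The second, smaller issue is the pairing of a median with an SD. The SD is computed about the mean and hides asymmetry, which is the usual reason for choosing a median. An interval for a mean difference cannot be rebuilt from medians and SDs.

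**Working it through.** **Inputs.** Arm sizes of 14 (placebo) and 18 (levothyroxine) come from Primary Outcome Measure. Adverse-event counts of 1 of 14 on placebo and 2 of 18 on levothyroxine come from the narrative under Method of Estimation. Its percentages, 7.14% and 11.11%, equal 1/14 and 2/18.

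**1. The plan's own interval, reproduced.**
- RR = (2/18)/(1/14) = 1.556.
- SE of log RR = sqrt(1/2 − 1/18 + 1/1 − 1/14) = 1.172.
- 95% CI = 1.556 × exp(±1.96 × 1.172) = 0.156 to 15.46; Fisher exact p = 1.0.

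This matches the printed 1.55 (0.15 to 15.47), p = 1.0, apart from truncation and 0.01 in the upper limit. The risk ratio therefore carries a proper precision measure even though the dispersion line above it says SD.

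**2. SD against standard error for the mean difference.** With a common SD s:
- SE = s × sqrt(1/14 + 1/18) = 0.3563 × s.
- SD/SE = 1/0.3563 = 2.81.
- 95% half-width = t(0.975, 30 df) × SE = 2.042 × 0.3563 × s = 0.728 × s.
- SD/half-width = 1/0.728 = 1.37.

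These ratios depend only on the arm sizes and hold for any common s.

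**3. What the missing interval might look like (illustration only).** No SDs of final values are given. Assume they equal the baseline SDs in Table 1, 1.28 (placebo) and 1.20 (levothyroxine) g/24 h.
- Pooled SD = sqrt((13 × 1.28² + 17 × 1.20²)/30) = 1.235.
- SE = 1.235 × 0.3563 = 0.440.
- Half-width = 2.042 × 0.440 = 0.90 g/24 h.

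For assumed SDs of 0.8 to 2.0 the half-width runs from 0.58 to 1.46 g/24 h. These figures reflect sample size and spread. They show what information is missing and do not measure harm done by the label.

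**4. Mean or median for the primary outcome.** Primary Outcome Measure asks for a mean with SD. The general rule in Statistical Test of Hypothesis and Method allows a median with SD for the same variable if its distribution calls for it. Under the first, arm means, SDs and sizes are reported and a t-based interval can be rebuilt. Under the second it cannot.

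**The case against.** The strongest reply is that the SD line is a form entry that was not applied literally: the one effect estimate actually printed, the risk ratio, has a correct 95% CI. The primary outcome entry also calls for means with SDs and gives arm sizes, so a reader could compute the interval. This stands as mitigation and keeps the point small. It does not remove it, because the plan still assigns an SD to the difference and still plans no interval for it.

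Three stronger readings are tempting, and the documents do not support them.

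- **That the entry is a mislabelled standard error, so readers would misjudge precision 2.8-fold.** The documents do not show whether the label is a copied arm-level entry or a misnamed SE. If it were an SE, the quantity would be suitable and only the word wrong. No mean difference or dispersion for it is printed, so no actual misreading can be shown.
- **That baseline proteinuria was tested by Mann-Whitney, so the median branch applies to the primary outcome.** A t test on the printed baseline values gives p = 0.34, against 0.14 in Table 1. Many other rows miss too (t test against printed): age 0.21 and 0.41, TSH 0.047 and 0.02, creatinine 0.022 and 0.05, cholesterol 0.80 and 0.67, hemoglobin 0.27 and 0.17, diastolic pressure 0.43 and 0.60. Systolic pressure agrees (0.165 and 0.17). The table names no test, so the mismatch says nothing specific about proteinuria.
- **That the mean difference must remain the primary estimate even when Mann-Whitney is the test.** That is a preference and does not follow from the error.

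**Conclusion.** The point holds as a minor estimation and reporting error. On the text, the SD is the wrong dispersion measure for the estimated mean difference, and no standard error or confidence interval is planned for that difference. The SD is also the wrong companion for a median.

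The size is 2.81 (SD to standard error) and 1.37 (SD to 95% half-width). Both rest on 14 and 18 analysed patients and a common SD; the second also uses the t distribution with 30 df. The half-widths in g/24 h rest on assumed final SDs and are illustrative.

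For the primary outcome the median issue is a tension between two sections, and a t-based interval can be rebuilt if the outcome entry is followed. The hypothesis tests, p-values and superiority decision do not change. SD remains correct for arm-level means.

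**What to change.** - **Method of Estimation:** replace the SD label with a 95% confidence interval for the between-arm mean difference, as is already reported for the risk ratio.
- **Statistical Test of Hypothesis and Method:** show means with SD and medians with the interquartile range.
- **Baseline table and outcome entries:** keep SD as the spread of arm-level means.
- **Optional:** where Mann-Whitney is used for a variable, a Hodges-Lehmann shift with its confidence interval may be added.

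The cost is a wording change in two sections and a short re-run on existing data. The trial is complete and no new data are needed. The downside is a little extra analysis, and a second effect estimate to explain if the Hodges-Lehmann shift is added.
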